10.6.4. Safety

10.6.4.1. CV Safety Endpoints

CV Safety Endpoints

Dates for Investigator Reported CV Safety Endpoints
 
 • All-cause hospitalization: admission date • Death: date of death from the Death1 eCRF page • Myocardial infarction: date of onset of Myocardial Infarction/Unstable Angina symptoms from the MI/UA1 eCRF page • Stroke: start date of neurological symptoms from the Stroke/TIA eCRF page • Hospitalization for HF: Earliest of (ER admission date, Hospital admission date) from Heart Failure eCRF page • Thromboembolic event: date of onset of thromboembolic event from the Thromboembolic Event eCRF page

Dates for Adjudicated CV Safety Endpoints
 
 • Death: event date reported by CEC • Myocardial infarction: event date reported by CEC 
 ○ Fatal MI events only identified through a primary cause of death, without a corresponding positively adjudicated MI event: death event date reported by CEC • Stroke: event date reported by CEC 
 ○ Fatal stroke events only identified through a primary cause of death, without a corresponding positively adjudicated stroke event: death event date reported by CEC • Hospitalization for HF: event date reported by CEC 
 ○ Fatal heart failure/cardiogenic shock events only identified through a primary cause of death, without a corresponding heart failure event: death event date reported by CEC • Thromboembolic event (DVT, PE, VAT): event date reported by CEC 
 ○ Fatal PE events only identified through a primary cause of death, without a corresponding positively adjudicated PE event: death event date reported by CEC 
Due to the design of the CRF, a fatal MI is reported as both an MI and a death. Both of these events will go through the adjudication process. It is possible that the MI could be negatively adjudicated, while the death is positively adjudicated with a primary cause of acute MI. The rationale for this is that the definition of a positively adjudicated MI (contained in the CEC charter) is more explicit than the definition of acute MI as a primary cause of death. Therefore, in analyses that include MI events without including all-cause mortality, the primary approach will be to include only those fatal MI events that correspond to a positively adjudicated MI event. These analyses will then be repeated for supportive purposes using all fatal MI events – including those fatal MI events only identified through a primary cause of death (i.e., acute MI) without a corresponding positively adjudicated MI event.
 
Additionally, a fatal MI event could have an event date that differs from the death date because the subject may have died as a result of the MI but not on the same day. For analysis of first occurrence MACE, MI or any other composite endpoint that includes both MI and death, if both

CONFIDENTIAL

201410

CV Safety Endpoints

the MI and death events are positively adjudicated, the MI date will be used as the event date. For analysis of CV mortality only and all-cause mortality only, the death date will be used.

Similarly, fatal stroke events are reported as both a stroke and a death. In analyses that include stroke events without including all-cause mortality, the primary approach will be to include only those fatal stroke events that correspond to a positively adjudicated stroke event. These analyses will be repeated for supportive purposes using all fatal stroke events – including those fatal stroke events only identified through a primary cause of death (i.e., stroke) without a corresponding positively adjudicated stroke event. For analysis of first occurrence MACE, stroke, or any other composite endpoint that includes stroke and death, if both the stroke and death events are positively adjudicated, the stroke date will be used as the event date. For analysis of CV mortality only and all-cause mortality, the death date will be used.

Fatal heart failure events are reported as both a heart failure and a death. In analyses that include hospitalization for heart failure events without including all-cause mortality, a single approach which includes only those fatal hospitalization for heart failure events that correspond to a positively adjudicated hospitalization for heart failure event will be used. The definition of the hospitalization for heart failure endpoint includes requirements around hospitalization which are not captured in the associated primary cause of death (heart failure/cardiogenic shock), so identification of hospitalization for heart failure events through only a primary cause of death is not possible. However, supportive analyses of the hospitalization for heart failure endpoint may include all heart failure events. These supportive analyses would then be able to include fatal heart failure events from the death page (i.e. primary cause of death = heart failure/cardiogenic shock) that do not correspond to a positively adjudicated heart failure event. For analysis of hospitalization for heart failure or any composite endpoint that includes hospitalization for heart failure and death, if both the hospitalization for heart failure and death events are positively adjudicated, the hospitalization for heart failure date will be used as the event date. For analysis of CV mortality only and all-cause mortality, the death date will be used.

Fatal pulmonary embolism events are reported as both a pulmonary embolism and a death. In analyses that include pulmonary embolism events (i.e., thromboembolic events) without including all-cause mortality, the primary approach will be to include only those fatal pulmonary embolism events that correspond to a positively adjudicated pulmonary embolism event. These analyses will be repeated for supportive purposes using all pulmonary embolism events – including those fatal pulmonary embolism events only identified through a primary cause of death (i.e., pulmonary embolism) without a corresponding positively adjudicated pulmonary embolism event. For analysis of pulmonary embolism or any composite endpoint that includes pulmonary embolism and death, if both the pulmonary embolism and death events are positively adjudicated, the pulmonary embolism date will be used as the event date. For analysis of CV mortality only and all-cause mortality, the death date will be used.

In the situation that there is a fatal MI (or fatal stroke, hospitalization for heart failure, or pulmonary embolism) that does not have both an MI(or stroke, hospitalization for heart failure, or pulmonary embolism) endpoint and a death endpoint reported, the date of the event that is reported will be used in the analysis of all relevant endpoints. This would additionally apply to situations where the MI (or stroke, hospitalization for heart failure, or pulmonary embolism) may occur within an analysis period and the death may occur outside of the analysis period; the endpoint with the date in the analysis period will be used for all relevant endpoints.

CV Safety Endpoints
Missing or Partial Endpoint Dates

Missing of Partial Event (Start) Dates
 
 • If event dates are missing or partial and there is not sufficient information to classify the time period of the event, the event will be classified as occurring on-treatment and post-randomization. The event will also be considered to have occurred during the follow-up for cardiovascular events as defined in Section 10.6.4. • The following rules for missing or partial event dates for events other than death will be implemented as long as the imputed date is after the randomization date. If the imputed date is prior to the randomization date, then the date of randomization will be imputed for the event date. 
 ○ If only the day of the month is missing, impute the first day of the month (e.g., --FEB2016 would impute as 01FEB2016) ○ If the month and day of the month are missing, impute 01JAN (e.g., ----2016 would impute as 01JAN2016) ○ If the year, month, and day of month are missing, impute the randomization date • The following rules for missing or partial death dates will be implemented as long as the imputed date is after the randomization date. If the imputed date is prior to the randomization date, then the date of randomization will be imputed for the death date. 
 ○ The latest clinic visit, telephone visit, other contact with subject visit, CV endpoint (other than death), AE or SAE date, or date last known to be alive will be determined. If the year, month, and day of month of the death are missing then the death date will be imputed as the latest of the dates. ○ If only the day of the month of death is missing, then impute the first day of the month (e.g., --FEB2016 would impute as 01FEB2016). However, if this imputed date results in a date that is prior to the latest clinic visit, telephone visit, other contact with subject visit, CV endpoint (other than death), AE or SAE date or date last known to be alive then impute the missing day of death as equal to this date instead. For example: 
 ▪ If --FEB2016 is given as the death date and there is a non-fatal MI on 08FEB2016, then the imputed date of death would be 08FEB2016 rather than 01FEB2016 such that the death is not before the non-fatal MI. ▪ If --MAR2016 is give as the death date and the latest date is a non-fatal MI on 08FEB2016 then the imputed date of death would be 01MAR2016. ○ If the month and day of the month of death are missing, then impute as 01JAN (e.g., ----2016 would impute as 01JAN2016). However, if this imputed date results in a date that is prior to the latest clinic visit, telephone visit, other contact with subject visit, CV endpoint (other than death), AE or SAE date, or date last known to be alive then impute the missing month and day of death as equal to this date instead. For example: 
 ▪ If ----2016 is given as the death date and the latest date is a non-fatal MI on 08FEB2016 then the imputed date of death would be 08FEB2016 rather than 01JAN2016 such that the death is not before the non-fatal MI.

CONFIDENTIAL

201410

CV Safety Endpoints

 
 ▪ If ----2017 is given as the death date and the latest date is a non-fatal MI on 08FEB2016 then the imputed date of death would be 01JAN2017. ○ For deaths that occur after subjects have prematurely withdrawn from the study, missing or partial dates will be imputed as specified above except if the imputation places the death prior to or on the premature withdrawal date. In this case the death date will be imputed as the premature withdrawal date. 
Missing or Partial Hospitalization End Dates
 
 • If hospitalization end dates are missing or partial, the following rules for missing or partial dates will be implemented as long as the imputed date is before the next hospitalization start date or study completion/withdrawal date (if there is no next hospitalization start date). If the imputed date is after the next hospitalization start date, then the date of the next hospitalization start date – 1day will be used as the hospitalization end date. If the imputed date is after the study completion/withdrawal date, then the date of the study completion/withdrawal date will be used as the hospitalization end date. 
 ○ If only the day of the month is missing, impute the last day of the month (e.g., --MAR2016 would impute as 31MAR2016) ○ If the month and day of the month are missing, impute 31DEC (e.g., ----2016 would impute as 31DEC2016) ○ If the year, month, and day of month are missing, impute the date of study completion/withdrawal.
Order of CV Safety Endpoint Events

 • If multiple events occur on the same day or have imputed dates that place them on the same day, but it is not clear which event occurred first, then the following order will be applied: 
 1. MI 2. Stroke 3. Hospitalization for Heart Failure 4. Thromboembolic Event: DVT 5. Thromboembolic Event: VAT 6. Thromboembolic Event: PE 7. Death
CV Mortality

 • CV mortality includes all deaths indicated as having a cardiovascular primary cause of death (including fatal MI and fatal stroke events) as well as deaths with an undetermined primary cause of death that are indicated to be either presumed sudden death or presumed cardiovascular death. Deaths with an undetermined primary cause of death that are indicated to be an unknown death will not be included as a CV mortality event.
Heart Failure Events

 • The primary heart failure event of interest in this study is hospitalization for heart failure. However, investigators are requested to report all potential heart failure events for adjudication, even if there was no hospitalization associated with the event. • The CEC will categorize heart failure events into one of the following adjudicated event types:

CONFIDENTIAL

201410

CV Safety Endpoints	

 ○ Hospitalization for Heart Failure ○ Urgent ER/ED Visit for Heart Failure ○ Urgent Office/Practice Visit for Heart Failure ○ Negative adjudication (i.e., not one of the heart failure events above) ● For purposes of endpoints that contain hospitalization for heart failure as a component, only the events adjudicated by the CEC as Hospitalization for Heart Failure will be included. ● The concordance table for heart failure events will include the 4 adjudicated event types listed above. 	
Investigator-reported Endpoint Events for Concordance	

 ● For purposes of concordance tables, events with an investigator-reported event date \geq randomization date during the time period for follow-up of cardiovascular events, that meet the following final diagnosis criteria will be considered to be investigator-reported endpoint events: 	
Endpoint	Investigator-reported final diagnosis (from eCRF)
Myocardial infarction	Myocardial infarction
Stroke	Primary ischemic stroke (with or without hemorrhagic transformation), Primary intracranial hemorrhage, Retinal/ocular hemorrhage or infarction, Unknown type of stroke
Hospitalization for Heart Failure	
Systolic heart failure, Diastolic heart failure, Heart failure - unspecified type
 
Additional criteria: If admission/discharge times are non-missing, at least one of the following must be true (1-3):
 
 1. Time in hospital is ≥ 24 hours 2. Time in ED/ER is ≥ 24 hours 3. Consecutive time in hospital + time in ED/ER is ≥ 24 hours 
Or if admission/discharge times are missing, then at least one of the following must be true (4-6):
 
 4. Change in calendar date between hospital admission and discharge 5. Change in calendar date between ED/ER admission and discharge 6. Change in calendar date between consecutive hospital and ED/ER admission and discharge
Thromboembolic Event (DVT, PE, VAT)	Deep Vein Thrombosis (DVT), Pulmonary Embolism (PE), Vascular Access Thrombosis
All-cause mortality	Any death record
CV mortality	Any Cardiovascular primary cause of death
Non-CV mortality	Any Non-Cardiovascular primary cause of death
All-cause Hospitalization	

 ● All-cause hospitalization events are defined to be hospital admissions recorded on the Hospitalization eCRF form with a hospitalization duration ≥ 24 hours. ● Hospitalization rate (per year) across the study = number of all-cause hospitalization events / [follow-up time (days) / 365.25]. 	

CONFIDENTIAL

201410

CV Safety Endpoints
General Definitions

 • Time to event (days) = date of event – randomization date +1 • Censored time (days) = censoring date – randomization date + 1

 • First event person years = (cumulative total time to first event for subjects who have the event + cumulative total of censoring time for subjects without the event) / 365.25 • First event incidence rate (per 100 person years) = (100 * number of subjects with at least 1 event) / first event person years • First event absolute rate difference (per 100 person years) = daprodustat incidence rate (per 100 person years) – darbepoetin alfa incidence rate (per 100 person years)

Evaluation Time Periods for CV Endpoints
Time Period for Follow-up of Cardiovascular Endpoints

The period for capturing CV safety endpoints begins at randomization. The end of this time period is the date of study completion/withdrawal, with the exception that if a death has been reported in the clinical database after this time, then the death will be included in the analysis.
 
Any endpoints that occurred before the start of this time period are considered to be prior to the time period for follow-up of cardiovascular safety events, and any endpoints that occurred after the end of this time period are considered to be post the time period for follow-up of cardiovascular safety endpoints.

Time Period for Vital Status

The period for capturing vital status begins at the date of randomization. The end of this time period is defined as follows:
 
 • For all subjects known to have died, use the date of death • For all subjects who complete the study, use the study completion date (see Section 10.6.1) • For all subjects who withdraw from the study, but vital status has been ascertained, and are known to have not died – use the latest date last known to be alive. If vital status has not been ascertained following study withdrawal, use the study withdrawal date. 
Any endpoints that occurred before the start of this time period are considered to be prior to the time period for vital status, and any endpoints that occurred after the end of this time period are considered to be post the time period for vital status.

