8.2.2.4. Planned Exploratory Cardiovascular Safety Analysis Details

Exploratory CV Safety Analyses
Endpoint(s)¹:

 • MACE (all-cause mortality, non-fatal MI, or non-fatal stroke) • MACE or a thromboembolic event • MACE or hospitalization for HF • All-cause mortality • CV mortality • MI (fatal and non-fatal) • Stroke (fatal and non-fatal) • CV mortality or non-fatal MI • All-cause hospitalization
Model Specification

 • For all exploratory CV endpoints, confidence intervals for the rate per 100 person-years will be reported. For within-group rates, the 95% CI will be obtained using an exact Poisson method. For difference in rates between treatments, the two-sided 95% CI will be constructed with a normal approximation using Walds' method [Liu, 2006]. • • For MACE endpoint, the calculation of time-to-event or censoring is described in further detail in Section 10.6.4.1. • First occurrence of adjudicated MACE for a subject is defined as the first adjudicated event, determined by the event date, which is indicated as all-cause mortality, non-fatal MI or non-fatal stroke with further details in Section 10.6.4.1. • For those endpoints or components of endpoints intended to go through the adjudication process, only the adjudicated results will be used.
Model Results Presentation

 • A summary of the number and percentage of subjects having first-occurrence MACE will be provided by treatment group. The number and percentage of the types of events that make up the first occurrence of MACE will also be provided by treatment group. This summary table will be repeated for MACE plus thromboembolic events, for MACE plus hospitalization for heart failure and for MACE plus thromboembolic events or hospitalization for CHF.

CONFIDENTIAL

201410

Exploratory CV Safety Analyses

- A summary of all MACE including the number and percentage of subjects and number of events (including first and subsequent MACE) by type of event will be provided by treatment group.
- A summary of the number and percentage of subjects having first-occurrence adjudicated COVID-19 MACE will be provided by treatment group. The number and percentage of the types of events that make up the first occurrence of adjudicated COVID-19 MACE will also be provided by treatment group.
- Summaries of adjudication details of all-cause mortality will include the number and percentage of subjects by cause of death.

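### Deaths reported after study completion or withdrawal count as CV events while event-free subjects stop contributing time there, which pushes MACE and other death-containing rates upward

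*SAP*

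**What the plan says.** SAP 10.6.4.1 defines two windows under its heading on evaluation time periods for CV endpoints.

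- **Follow-up of cardiovascular endpoints.** It opens at randomization. "The end of this time period is the date of study completion/withdrawal", with one exception: "if a death has been reported in the clinical database after this time, then the death will be included in the analysis".
- **Vital status.** It also opens at randomization. Its end depends on the subject: "For all subjects known to have died, use the date of death"; "For all subjects who complete the study, use the study completion date"; for withdrawn subjects found to be alive, "use the latest date last known to be alive"; for withdrawn subjects whose status was not ascertained, the withdrawal date.

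The general definitions in the same section set the incidence rate as 100 times the number of subjects with an event, divided by first-event person-years. Those person-years are the time to first event plus the "cumulative total of censoring time for subjects without the event". The formula is "Censored time (days) = censoring date – randomization date + 1", and the censoring date is not defined further, so the window has to supply it.

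SAP 8.2.2.4 lists MACE, the MACE composites, all-cause mortality and CV mortality. It plans within-group rates with exact Poisson intervals, rate differences with normal-approximation intervals, and a Kaplan-Meier display for MACE. For MACE it says that "the calculation of time-to-event or censoring is described in further detail in Section 10.6.4.1". Neither section says which window belongs to which endpoint.

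**The concern.** Take two subjects who withdraw on the same day and whose status is checked on the same later day. One has died and the other is alive. Under the CV window the first adds an event and the time up to it. The second adds nothing after withdrawal. Whether later follow-up counts depends on its result, so the numerator is extended without the matching denominator. The same selection acts on the Kaplan-Meier risk set, which keeps late decedents and drops survivors seen just as late.

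The case is expected to arise. SAP 10.6.4.1 has a rule for dating deaths after premature withdrawal when the date is missing or partial; if imputation lands on or before withdrawal, the death is placed at withdrawal and adds an event with no further time. Protocol 5.6.1 has vital status sought from available sources after consent is withdrawn, while Protocol 7.4.3.1 does not oblige investigators to look actively for events in former subjects.

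At stake are the absolute mortality and MACE rates, which are planned safety outputs and likely to be compared with rates from elsewhere.

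**Working it through.** **Figures in the plan.** The documents state no mortality, MACE or study-withdrawal rate. Protocol 9.4.4.1 says only that fewer than 80 first MACE are expected, which cannot be reproduced without a rate. Over an assumed 250 to 330 person-years (PY), 80 events would be 80/250 = 32 to 80/330 = 24 per 100 PY, as a ceiling.

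**Assumed inputs.** Constant hazard λ of 5 to 20 per 100 PY; a share w of 3 to 20% withdrawing at C_w = 0.5 year; a share a of 50 to 100% of withdrawn subjects later ascertained over H = 0.6 year; completion at C_c = 1.08 years.

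**Formulas, per subject.** Let S_w = exp(−λC_w), S_c = exp(−λC_c), D = 1 − exp(−λH) and E = [1 − exp(−λH)(1 + λH)]/λ.

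- Withdrawn, CV window: events 1 − S_w + S_w·a·D; time (1 − S_w)/λ + S_w·a·E.
- Withdrawn, Vital Status window: the same events; time increased by S_w·a·(1 − D)·H.
- Completer, no late deaths: events 1 − S_c; time (1 − S_c)/λ.

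**Example: λ = 0.10, w = 5%, a = 1.**

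- S_w = 0.9512, D = 0.0582, E = 0.0173, S_c = 0.8976.
- Withdrawn: events 0.0488 + 0.9512 × 0.0582 = 0.1042; time 0.4877 + 0.9512 × 0.0173 = 0.5042.
- Completer: events 0.1024; time 1.0237.
- CV window: (0.05 × 0.1042 + 0.95 × 0.1024)/(0.05 × 0.5042 + 0.95 × 1.0237) = 0.10246/0.99775, or 10.27 per 100 PY (+2.7%).
- Vital Status window: add 0.05 × 0.9512 × 0.9418 × 0.6 = 0.0269 to the time. The rate is 0.10246/1.02462, or 10.00 (0.0%).

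**Range, with no late completer deaths.**

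| True rate per 100 PY | 3% withdrawn, half ascertained | 5%, all ascertained | 20%, all ascertained |
|---|---|---|---|
| 5 | 5.04 (+0.8%) | 5.14 (+2.8%) | 5.60 (+12.1%) |
| 10 | 10.08 (+0.8%) | 10.27 (+2.7%) | 11.17 (+11.7%) |
| 20 | 20.15 (+0.8%) | 20.51 (+2.5%) | 22.19 (+11.0%) |

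The Vital Status window gives 0.0% in every cell. The model uses one hazard and treats every event as a death. In a composite only the fatal part is picked up after withdrawal, so the relative inflation shrinks roughly with the fatal share.

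**Completers.** Suppose a share q of deaths in the half year after completion is reported. In the example with q = 5%, under the Vital Status window, events rise by 0.95 × 0.8976 × 0.05 × 0.0488 = 0.00208 and time by 0.95 × 0.8976 × 0.05 × 0.0121 = 0.00052. The rate is 0.10454/1.02514, or 10.20 (+2.0%). Across the grid with q of 5 to 20%, that window still gives +1.5% to +8.6%, because completers' time stops at completion while their deaths do not.

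**Between arms.** With equal hazards and assumed withdrawal of 5% against 15% (a = 1), the CV window creates a false difference of 0.30, 0.58 and 1.09 per 100 PY at true rates of 5, 10 and 20. The standard error of the difference, at an assumed 150 PY per arm, is 100·√(2 × λ × 150)/150, which is 2.6, 3.7 and 5.2.

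**The case against.** **The Vital Status window may already govern mortality.** It sits under the same heading, is worded as an endpoint window, and credits withdrawn subjects known to be alive. A reader might infer that survivors' later follow-up is never counted and that all mortality rates are biased. The documents do not support that. They equally do not say that mortality uses this window, so bias in mortality is possible but not established. For MACE and the other composites the CV window is the one written for them.

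**Leaving out known deaths has a cost.** If subjects withdraw because they are deteriorating, censoring at withdrawal is informative and pulls rates down. A subject could also be dead in the mortality table and event-free in the main MACE table. This stands as a drawback, and it is why the late deaths should still be shown.

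**The size is assumed.** Protocol 5.6.1 expects consent withdrawal to be rare. Protocol 5.5.1 keeps subjects in the study when they are followed by other agreed means. The 30% in Protocol 9.2.1 is treatment discontinuation, not study withdrawal. The low end of the range may be nearer the truth.

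**The analysis is exploratory.** Protocol 9.4.4.1 says the study is not powered for CV safety, and no hypothesis test is planned. SAP 8.2.2.4 also describes the Kaplan-Meier time as running to first MACE or the end of the trial, so the censoring of that curve is not fully pinned down. Both points limit the weight of the finding. Neither makes the rule symmetric.

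**Conclusion.** Followed as written, the CV follow-up window makes follow-up depend on outcome and biases the absolute rates, their intervals and the Kaplan-Meier curve upward for MACE and other composites containing death. All-cause and CV mortality share the bias only if that window governs them, which the SAP leaves open.

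The inflation is about 1 to 12% under assumed withdrawal of 3 to 20%, with no late completer deaths. The upper figures need high withdrawal, complete ascertainment and events that are all deaths.

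Two stronger readings should be avoided. One is that the Vital Status window treats deaths and survivors alike: it does so for withdrawn subjects whose status is known, but not for completers, and not if deaths are found more readily than survival is confirmed. The other is that the open-label design biases the comparison of arms. Nothing in the documents shows that withdrawal or late reporting differs by arm, and even the assumed 5% against 15% gives a false difference well below its standard error.

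The SAP should be corrected, but the point does not touch the primary or principal secondary analysis.

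**What to change.** 1. **MACE and other composites.** In the main analysis, end both events and person-time at study completion or withdrawal for every subject. Show deaths reported later in a sensitivity analysis.
2. **All-cause and CV mortality.** State that the Vital Status window applies, so that withdrawn subjects known to be alive are credited to the date they were last known alive. Do not count completers' deaths after the completion date in the main rate; show them in the sensitivity analysis. Events and person-time then share one cut-off.
3. **Definitions.** Name the window for each endpoint in SAP 8.2.2.4, define the censoring date explicitly in 10.6.4.1, and use the same date for the Kaplan-Meier display.

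The cost is SAP wording and one extra sensitivity table. No new assessments are needed, though last-known-alive dates may be missing for some withdrawn subjects; the SAP already ends those at withdrawal. The drawbacks are that a few late deaths leave the main table and that censoring at withdrawal may be informative, so the sensitivity table should be reported beside the main one.
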